- have had substance use disorder (other than alcohol or nicotine) in the preceding 3 months
- are currently imprisoned or in psychiatric hospitalization

Table 1. Study Procedures

| Session # | Location of Visit | Procedures | Payment |
|-----------|-------------------|---|---------|
| 1 | Lab | Consent; psychiatric interview; questionnaires; urine drug screen and pregnancy test; carbon monoxide and breath alcohol readings | \$50 |

| 1-3 weeks | | | |
|-------------------------------------|-------|---|--|
| 2 | Phone | Counseling session 1 of 4 | n/a |
| 1 week | | | |
| 3 | Phone | Counseling session 2 of 4; begin practice mCM monitoring, begin bupropion if eligible | Up to \$34 for monitoring |
| 1 week | | | |
| 4 | Phone | QUIT DATE; counseling session 3 of 4; begin active mCM monitoring OR active mobile monitoring (MM); begin nicotine replacement therapy (NRT) | n/a |
| 2 weeks | | | |
| 5 | Phone | Counseling session 4 of 4; continue active mCM monitoring OR active mobile monitoring | n/a |
| 1 week | | | |
| 6 | Phone | Final week of abstinence induction in mCM group; MM group continues monitoring; questionnaires | Up to \$702 (mCM) OR \$132 (MM) for active monitoring; |
| | | | \$50 for assessment |
| 2 weeks | | | |
| 7 | Lab | End thinning (mCM group) OR mobile monitoring (MM group); return equipment; questionnaires; end NRT and bupropion; saliva sample; interview about treatment | Up to \$400 (mCM) OR \$88 (MM) for continuing monitoring |
| | | | \$35 for equipment return; \$50 for assessment; \$50 for saliva sample |
| 6 months after Session 4 | | | |
| 8 | Lab | Questionnaires; saliva sample; blood spot collection | \$50 for assessment and \$50 for saliva sample; \$50 for blood spot test |
| TOTAL COMPENSATION POSSIBLE: | | mCM Group Mobile Monitoring | \$1521* \$639* |

*because compensation depends partly on the number of alcohol breathalyzer prompts, it is possible that the total compensation will vary slightly.

Consent and Screening Procedures

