Pharmacotherapy for Smoking Cessation

Treatment will include standard pharmacotherapy for smoking cessation. This consists of bupropion, nicotine patch, and an 8-week course of < 2 rescue methods (e.g., nicotine gum, lozenge) in participants for whom these medications are not contraindicated or who receive medical clearance from a physician. Participants will be screened for suitability for NRT or other smoking cessation medication. Participants who report being contraindicated to bupropion or NRT (i.e. high blood pressure not controlled by medication) must obtain authorization from their physician prior to receiving the corresponding medication. If the patient does not have a physician, or the physician does not respond to information requests, [name] will make determinations about whether to authorize study medications. [name] will prescribe a tailored amount and delivery type of NRT based on number of cigarettes smoked per

day, quit history, medical conditions, and psychiatric comorbidities. NRT and bupropion will be provided *via* mail. [name] will write the NRT and/or bupropion prescriptions and work with other study staff and participants' primary care physician to discuss contraindications. Eligible participants will be provided bupropion for eight weeks. Participants will be informed that they can discuss whether or not to continue bupropion use for relapse prevention with their personal physician. At the end of the study's course of bupropion, participants will be reminded to confer with their physician re: continued bupropion use. For participants who relapse to smoking or are unable to quit, [name] will make decisions about whether to prescribe additional NRT to assist the participant in their continued attempts to stop smoking.

6-Month Follow-Up

All participants will be asked to provide a saliva sample to bioverify smoking abstinence. Alcohol abstinence will be measured by self-report, breathalyzer, and a blood spot sample that measures PEth at the 6-month follow-up. Participants will be encouraged to attend the 6-month follow-up assessment in the lab. However, if participants are unable due to transportation issues or decline to attend the 6-month follow-up, we will administer interview and questionnaire measures by phone and collect saliva samples by mail.

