Self-efficacy will be assessed with the Alcohol Abstinence Self-Efficacy Scale for alcohol (DiClemente, Carbonari, Montgomery, & Hughes, 1994) and the Relapse Situation Efficacy Questionnaire for smoking (Gwaltney, 2001). Motivation for smoking cessation will be measured with the Motivation to Stop Scale (Kotz, Brown, & West, 2013). Attitudes toward behavior change with respect to alcohol and smoking behavior will be measured with a brief measure of self-efficacy for quitting alcohol and the Readiness to Change Questionnaire (Heather, Rollnick, & Bell, 1993; Rollnick, Heather, Gold, & Hall, 1992). In addition, confidence to keep from smoking when craving, facing social pressure, or experiencing negative emotion will be measured with the Self Efficacy to Overcome Personal Barriers to Cessation scale (Velicer, DiClemente, Rossi, & Prochaska, 1990). Affective states will be measured with the Positive and Negative Affect Scale (Watson, Clark, & Tellegen, 1988). Sleep disturbance will be measured with the Insomnia Severity Index (Morin, Belleville, Belanger, & Ivers, 2011). These measures will be administered at the baseline visit and administered by phone by study staff at the end of Abstinence Induction mCM, end of Thinning mCM, and 6-month follow-up assessments. At the end of Thinning mCM study session, we will ask participants to report on any problems with CO monitoring, especially regarding the validity of monitoring. All phone counseling sessions will include assessment of alcohol consumption and smoking behavior over the past week, as well as readiness to change and self-efficacy measures for alcohol and smoking.

Process measures will include number of telephone counseling sessions completed and medication adherence. Medication adherence will be defined as using > 80% of prescribed medications, as 80% adherence to NRT has been predictive of doubled abstinence at 6 months (Catz et al., 2011). The primary self-report measure of adherence will be the number of days NRT is used during the study period. Days of NRT use will be recorded at each telephone counseling call. Participants will also be screened for NRT or other smoking cessation aid use at each follow-up. Participants will complete the Voils Medical Adherence Questionnaire to measure adherence to smoking pharmacotherapy. We will measure patient satisfaction with a questionnaire tailored to this study's treatment aims.

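### Bupropion and rescue NRT are 8-week courses in the text, but Table 1 ends them after 6 and 5 weeks

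*Combined protocol and SAP*

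**What the plan says.** Two places in the combined protocol and SAP set the length of the drug courses.

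- **Text.** Pharmacotherapy for Smoking Cessation describes the regimen: "This consists of bupropion, nicotine patch, and an 8-week course of < 2 rescue methods", with gum and lozenge as examples of rescue methods. It later adds: "Eligible participants will be provided bupropion for eight weeks". It also requires that participants be reminded, when the study's bupropion course ends, to take up continued use with their own physician.
- **Table 1 (Study Procedures).** The Session 3 row has "begin practice mCM monitoring, begin bupropion if eligible". NRT starts in the Session 4 row, which is the quit date. The Session 7 row has "return equipment; questionnaires; end NRT and bupropion; saliva sample; interview about treatment".

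A third section depends on the course length. Treatment Process Measures states: "Medication adherence will be defined as using > 80% of prescribed medications". It gives no number of days for the denominator. It names days of NRT use over the study period as the main self-report measure, and does not define that period.

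**The concern.** The start and stop points in Table 1 do not span the eight weeks in the text. One protocol thus gives two lengths for a prescription drug and two for the rescue NRT. At stake are how much is supplied, when participants are told to stop, and whether the end-of-course reminder falls at a scheduled contact. The adherence rule needs a day count per medication, and the plan currently offers no single count to use.

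**Working it through.** **Inputs**

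- Text durations (Pharmacotherapy for Smoking Cessation): bupropion 8 weeks; rescue methods 8 weeks; patch not stated.
- Table 1 intervals: Session 1 to 2, 1 to 3 weeks; 2 to 3, 1 week; 3 to 4, 1 week; 4 to 5, 2 weeks; 5 to 6, 1 week; 6 to 7, 2 weeks.
- Table 1 start and stop: bupropion Session 3 to 7; NRT Session 4 to 7.
- Cross-check: the mCM Intervention section places the end of Thinning, which is Session 7, five weeks after the quit date. It sets the quit date at the end of the practice week.

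**Step 1: try to reproduce the 8 weeks from Table 1**

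- Bupropion, Session 3 to 7: 1 + 2 + 1 + 2 = 6 weeks (42 days).
- NRT, Session 4 to 7: 2 + 1 + 2 = 5 weeks (35 days). This agrees with the cross-check.
- Start at Session 2 instead: 1 + 6 = 7 weeks.
- Start at Session 1 instead: (1 to 3) + 7 = 8 to 10 weeks.

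Only a start at Session 1 with the shortest allowed gap gives 8 weeks, and Table 1 starts neither drug there. The stated figure is not reproduced.

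**Step 2: size of the conflict**

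| Medication | Text | Table 1 | Difference |
|---|---|---|---|
| Bupropion | 8 weeks (56 days) | 6 weeks (42 days) | 2 weeks |
| Rescue NRT | 8 weeks (56 days) | 5 weeks (35 days) | 3 weeks |
| Patch | not stated | 5 weeks (35 days) | no conflict |

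**Step 3: where the 8-week courses would end**

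- Bupropion starts 1 week before the quit date, so it would end at 8 − 1 = 7 weeks after it. That is 7 − 5 = 2 weeks after Session 7.
- Rescue NRT starts on the quit date, so it would end 8 weeks after it. That is 8 − 5 = 3 weeks after Session 7.
- The next row of Table 1 is Session 8, 6 months after Session 4. On the Table 1 reading the bupropion reminder coincides with a laboratory visit. On the 8-week reading it falls where Table 1 lists no contact.

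**Step 4: the adherence rule**

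The threshold is 0.80 × the days prescribed, and the plan states no such day count.

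- Bupropion: 0.80 × 56 = 44.8 days, or 0.80 × 42 = 33.6 days.
- Rescue NRT: 0.80 × 56 = 44.8 days, or 0.80 × 35 = 28 days.

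The number of days a participant must use the drug to count as adherent therefore depends on which course length is taken as prescribed.

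**The case against.** Several points on the other side stand. The amount and delivery type of NRT are tailored by one prescriber, who also writes the bupropion prescriptions, so there may be less divergence in practice than the documents suggest. Both arms have the same access to pharmacotherapy, so no between-arm bias is evident. The primary endpoint is at 6 months, after either scheduled course has ended. Adherence is a process measure, and Data Analyses describes no analysis that uses the 80% classification. None of this explains why the text says eight weeks and the table six or five. The provision for additional NRT covers participants who relapse or cannot quit, so it does not account for the standard course either.

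A reader might infer more, but the documents do not support these three extensions:

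- *That all NRT is an 8-week course in the text.* The wording attaches the 8 weeks to the rescue methods only.
- *That NRT exposure at the Session 7 saliva sample depends on which place is followed.* Table 1 puts the end of NRT and the sample at the same visit, and on the 8-week reading rescue NRT is still in use then. The readings diverge only after the sample, so reconciling them would not change how that cotinine result is read.
- *That full users would be misclassified*, because 42/56 = 75% and 35/56 = 62.5% both fall below 80%. Those ratios take the numerator from Table 1 and a denominator from the text that the adherence rule never states. If the prescription ends at Session 7, full use is 100%; if it runs eight weeks, stopping at Session 7 is not full use. What can be said is that the denominator is unspecified.

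**Conclusion.** The contradiction holds: 8 against 6 weeks for bupropion and 8 against 5 weeks for rescue NRT. For the patch there is a gap rather than a conflict, because the text gives no duration. The practical consequences are supply, the stopping point, the timing of the bupropion reminder and the unstated adherence denominator. Severity is moderate; no effect on the 6-month primary endpoint or on the comparison between arms has been shown.

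The conclusion assumes that the session intervals in Table 1 are the intended schedule, which the five-week figure in the mCM Intervention section supports. The absence of contact after Session 7 is also taken from Table 1. Data Analyses mentions a 6-week follow-up that the table does not list. If that were a contact 6 weeks after the quit date, it would still come before the end of an 8-week bupropion course at 7 weeks.

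**What to change.** Reconcile Table 1 with Pharmacotherapy for Smoking Cessation so that bupropion, patch and rescue NRT each have one start point and one stop point, stated identically in both places. Tie the end-of-course bupropion reminder to that stop point, and say at which contact it is given. In Treatment Process Measures, state the reconciled number of days for each medication as the denominator of the 80% rule. Which duration is right is for the sponsor and study physician to decide.

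The cost is a short amendment: a table row or a sentence, plus a stated day count per medication. It needs no additional participants. If the reconciled bupropion course runs past Session 7, the reminder will also need a contact that Table 1 does not now list.

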***BL=baseline; CBT= phone counseling sessions, PT=post-treatment/thinning; EM=end of monitoring; FUP= 6-month follow up**

To assist in evaluating potential study exclusion for the alcohol withdrawal criterion, we have adapted the Clinical Institute Withdrawal Assessment for Alcohol to ask about any recent periods of time in which potential participants have abstained from alcohol (Sullivan et al., 1989). This will be administered at the screening session. Demographics information will be collected at the screening session, and the OSS will be administered at the screen, end of monitoring, and 6 month follow up to measure changes in occupation status and household income.

Smoking-Related Measures

The Fagerström Test of Nicotine Dependence (Heatherton, Kozlowski, Frecker, & Fagerström, 1991), Questionnaire on Smoking Urges (Tiffany & Drobes, 1991), the Minnesota Nicotine Withdrawal Scale (Patten & Martin, 1996), and a smoking history questionnaire (e.g., number of cigarettes smoked/day, age of first smoking, number of previous quit attempts) will be used to measure smoking behaviors at baseline. In addition, the FTND, QSU, Dimensions of Anger Reactions, and Patient Health Questionnaire will be administered at the end of Abstinence Induction, end of Thinning mCM, and 6-month follow-up. Participants will also report number of cigarettes smoked each day, and days of smoking abstinence.

Participants will be asked to respond to several questions to determine if the patient is contraindicated to receive NRT. Collection of alcohol and smoking use data will allow calculation of dual abstinence days and longest duration of dual abstinence. The Cigarette Purchase Task will be used to evaluate the behavioral economics of cigarette use (MacKillop et al., 2008), and the Alcohol Purchase Task will evaluate the same for alcohol use (Acuff & Murphy, 2017). At five time points (baseline, quit date, end of abstinence induction, end of treatment, 6 month follow-up), participants will complete the Smoking Consequences Questionnaire, the Penn Alcohol Craving Questionnaire (Flannery et al., 1999), and the Alcohol Expectancies measure (Lee et al., 2015).

Treatment Process Measures

Self-efficacy will be assessed with the Alcohol Abstinence Self-Efficacy Scale for alcohol (DiClemente, Carbonari, Montgomery, & Hughes, 1994) and the Relapse Situation Efficacy Questionnaire for smoking (Gwaltney, 2001). Motivation for smoking cessation will be measured with the Motivation to Stop Scale (Kotz, Brown, & West, 2013). Attitudes toward behavior change with respect to alcohol and smoking behavior will be measured with a brief measure of self-efficacy for quitting alcohol and the Readiness to Change Questionnaire (Heather, Rollnick, & Bell, 1993; Rollnick, Heather, Gold, & Hall, 1992). In addition, confidence to keep from smoking when craving, facing social pressure, or experiencing negative emotion will be measured with the Self Efficacy to Overcome Personal Barriers to Cessation scale (Velicer, DiClemente, Rossi, & Prochaska, 1990). Affective states will be measured with the Positive and Negative Affect Scale (Watson, Clark, & Tellegen, 1988). Sleep disturbance will be measured with the Insomnia Severity Index (Morin, Belleville, Belanger, & Ivers, 2011). These measures will be administered at the baseline visit and administered by phone by study staff at the end of Abstinence Induction mCM, end of Thinning mCM, and 6-month follow-up assessments. At the end of Thinning mCM study session, we will ask participants to report on any problems with CO monitoring, especially regarding the validity of monitoring. All phone counseling sessions will include assessment of alcohol consumption and smoking behavior over the past week, as well as readiness to change and self-efficacy measures for alcohol and smoking.

Process measures will include number of telephone counseling sessions completed and medication adherence. Medication adherence will be defined as using > 80% of prescribed medications, as 80% adherence to NRT has been predictive of doubled abstinence at 6 months (Catz et al., 2011). The primary self-report measure of adherence will be the number of days NRT is used during the study period. Days of NRT use will be recorded at each telephone counseling call. Participants will also be screened for NRT or other smoking cessation aid use at each follow-up. Participants will complete the Voils Medical Adherence Questionnaire to measure adherence to smoking pharmacotherapy. We will measure patient satisfaction with a questionnaire tailored to this study's treatment aims.

At the end-of-treatment visit, each participant will complete a qualitative interview aimed at gathering detailed information on strengths, weaknesses and general user interface components of the intervention. The interview will vary in length, but we expect approximately 30 minutes for participants to provide detailed feedback on the intervention in this interview.

Participants will complete the computerized delay discounting task for hypothetical monetary values. They will choose between a fixed amount with fixed delay and various monetary amounts available immediately (Garcia-Rodriguez, Secades-Villa, Weidberg, & Yoon, 2013). Delays and monetary options will be presented in ascending order and adjusted with procedures that successively approximate an indifference point. The delay discounting task will be administered by smart phone app at the baseline screening session, the end of Abstinence Induction mCM, end of Thinning mCM, and 6-month follow-up. To assess the impulsivity mechanism more broadly, we will administer two self-report measures of impulsivity and disinhibition at baseline, end of Thinning mCM, and 6-month follow-up: the Conners' Adult ADHD Scale, and the Barratt Impulsivity Scale (BIS-15; Spinella, 2007). We will also administer 3 computerized tasks at office visits occurring at baseline, end of Thinning mCM, and 6-month follow-up: the Conners Continuous Performance Test, the Iowa Gambling Task (Bechara et al., 1994), and the Balloon Analogue Risk Task (Lejuez et al., 2002). Anxiety sensitivity will also be measured at baseline, end of monitoring, and 6-month follow-up using the Anxiety Sensitivity Index-Revised 36 (Taylor & Cox, 1998). Because nonsuicidal self injury (NSSI) is not uncommon in persons with alcohol use disorders, especially those with other comorbid psychiatric diagnoses, we would like to include a brief measure of NSSI at several time points in the study, i.e., baseline and follow-up visits. This measure will be administered to all participants at these time points. Participants can refuse to complete the measure. However, in our laboratory's experience, participants typically do not take issue with completing this brief measure.

Treatment Fidelity and Therapeutic Alliance Measurement

We will utilize a revised version of the Yale Adherence and Competence Scale system to measure counselor adherence in delivering behavioral treatments for substance abuse disorders (Carroll, 2000). The system includes checklists for measuring critical treatment

elements. A random selection of 20% of the counseling sessions will be recorded and rated for counselor fidelity/adherence. Audio recordings of these sessions will be made using an iPad or iPhone (see “Protection Against Risk and Data Security Measures” herein for additional information); only the therapist’s voice will be recorded during the conversation. To measure therapeutic alliance, the 16-item Individual Treatment Alliance Scale Revised Short Form (ITASr-SF) will be utilized. The ITASr-SF has been shown to be related to treatment dropout and treatment response in behavioral interventions (Pinsof, Zinbarg, & Knobloch-Fedders, 2008). This will be administered during the end of Abstinence Induction mCM phone session.

Potential Risks

There is a risk of discomfort or distress in answering questions on the study measures. However, distress and discomfort related to questionnaire completion is usually temporary and well-tolerated. Risks also include discomfort related to alcohol withdrawal and quitting smoking. Symptoms of alcohol withdrawal may include headache, insomnia, sweating, shakiness, and rarely, seizures or hallucinations. We will minimize risk of alcohol withdrawal by screening participants at high risk for withdrawal out of the study. However, in case enrolled patients experience alcohol withdrawal that is not reported at the screening visit, we will instruct patients to report symptoms to research staff. The physician prescriber will have the flexibility to adjust medications as needed to account for changes in clinical variables such as withdrawal, craving, and smoking lapse pattern. Participants will be encouraged to utilize emergency resources at Duke as needed to address these symptoms.

Quitting smoking may cause difficulty concentrating, poor sleep, increased appetite, anxious or depressed mood, and craving for cigarettes. Participants will be offered NRT, and there are risks associated with the use of NRT. Minimal risks associated with wearing a nicotine patch include skin irritation, dizziness, lightheadedness, increased heart rate or blood pressure, nausea or vomiting. If a participant indicates a contraindication to NRT (e.g. uncontrolled hypertension), medical clearance for NRT will be sought from the participant’s primary care physician and/or the study physician. If a participant with a seizure disorder, history of or current hepatitis and/or cirrhosis, renal impairment, and/or uncontrolled diabetes wishes to enroll in the study, he/she will not receive contraindicated medications.

Participants who are medically eligible will also be prescribed bupropion SR. Risks of bupropion use include dry mouth, insomnia, nausea, constipation, headache, shakiness or jitteriness, skin rash, sweating, allergic reaction, change in appetite, weight loss, dizziness, tremor, thinking abnormally, hot flashes, worsening depression or suicidal thoughts and behavior, and ringing in the ears. At the highest dosage of bupropion to be used in this study, seizures occurred in 1 out of every 1000 (0.1%) who took this drug. Participants are informed that they are not required to take bupropion, and will be allowed to participate in the study if they refuse to do so.

There is a potential risk associated with the loss of confidentiality of study data. Specifically, collection and transfer of videotaped carbon-monoxide monitoring have risks with regards to privacy and confidentiality. Please see “Protection Against Risk and Data Security Measures” for details on reduction of risk with regards to the proposed videotaping.

Protection Against Risk and Data Security Measures

While participants may benefit from quitting smoking and alcohol use, there are no guaranteed benefits to the individual participant and no immediate benefits of the proposed research to others. There are potential benefits to others from the information generated that potentially will be helpful in developing new combined treatments for smoking and alcohol use. In our opinion, the anticipated benefits of this study outweigh the potential risks.

The study is completely voluntary and participants are informed that they are free to refuse to answer any items on the questionnaires or questions from the interview that they do not wish to answer. They are also informed that they are free to decline participation in any procedure and can withdraw from the study at any time.

Potential risks will be minimized by carefully screening potential participants according to the inclusion/exclusion criteria, closely monitoring symptom levels, and following established laboratory procedures associated with participant safety.

If at any laboratory visit the participant’s breathalyzer results are above the legal limit and he/she has driven to the appointment, we will advise the participant not to drive home. We will encourage him/her to use the local bus system, call for someone to pick him/her up, or call a taxi. The study coordinator will help the participant to make these telephone calls. However, due to budgetary limitations, the study will not provide monetary assistance to these participants who require alternative transportation methods. If a participant is unwilling to arrange alternate transportation, we will encourage him/her to remain at the medical center for a period of time until he/she does not meet legal criteria for intoxication. If a patient does not wish to remain at the medical center, and voices intent to drive a vehicle while intoxicated, we will notify the Duke police.

We will be providing the study phones to participants for the course of the monitoring period and will retrieve them at the conclusion of monitoring. We will restrict access to the following applications: internet browsers, installation of apps, deletion of apps, and in-app purchases. We will prevent access to music, podcasts, movies, TV shows, apps, and other websites. We will prevent ability to change the following: accounts, cellular data use, background app updates, location services, contacts, calendars, reminders, photos, Bluetooth sharing, microphone, Twitter, Facebook, and advertising. We will

have the ability to remote wipe the phones if they are not returned. We will encourage participants via consent to only enter information on the phone that they are comfortable with sharing with the entities listed below.

Regarding mobile information security, we have taken care in previous projects using similar methods and technology to develop procedures to limit the risk of breach of confidentiality and privacy. For example, the smart phone is programmed such that a staff member will set up the telephone and enter the participant's code into the phone. When uploading a video, participants upload directly from the phone to an approved website that has been vetted by Duke's information security officers, and the phone programming ensures that the video is uploaded into the correct participant's area of the website. This ensures that study participants' data is stored in the correct place, and that study participants cannot view any other participants' data. Participants are asked to review their videos before posting, and they can choose not to upload any video that they don't wish to upload for any reason. In previous studies that have been run using this methodology, we have had no participant complaints regarding issues of privacy and confidentiality related to use of the smart phone videotaping procedures. In order to enhance participants' privacy, we will restrict access to several of the telephone's ancillary applications, and we have the ability to remotely delete data from any phones that are not returned to the study team.

For the study's website, we will use shared server space provided by InMotion Hosting, Inc (website www.[name].com). We will be using AES-256-CBC encryption with SHA1 for message authentication and RSA as the key exchange mechanism. The video recordings will be collected on devices that are FIPS-140-2 compliant. The data at rest at InMotion Hosting is AES-256 encrypted at rest, and the data being transferred are encrypted at transfer (AES-256). Data will be unencrypted only by study staff members who have access to the secured server at InMotion Hosting; the encryption key is held only by our staff. This will ensure all video uploads and data that the participant sends over the internet via their phones will only be transferred over encrypted network connections, essentially nullifying the possibility of someone gaining access to the video before it reaches our server. InMotion also runs audits regularly of the websites hosted within their shared servers to prevent scriptside vulnerabilities, as well as having a 24/7 support team monitoring their servers. The web application written for this study has been checked for SQL injection, Code Injection, XSS, and RFI vulnerabilities and has passed. The site will only be accessible by the study participants and the study coordinators via 512-bit SHA-2 hashed passwords.

In previous studies using this methodology that have been run in the Traumatic Stress and Health Research Laboratory, we have had no participant complaints regarding issues of privacy and confidentiality related to use of the smart phone videotaping procedures. As security controls have not been validated for InMotion Hosting, we will include a statement in the informed consent that the data/videos voluntarily submitted will be sent to InMotion and are no longer covered by Duke privacy protections.

